11.3.3.3 Histology-Agnostic Biomarker Negative Stopping Rule

If a histology-specific biomarker negative cohort has completed accrual and there are fewer than 2 responses observed, and there have not been any responses observed in the histology-agnostic biomarker-negative expansion cohort (if open), then the histology-agnostic biomarker negative cohort will not open to accrual or will close to accrual if open. In this circumstance, patients from the histology-specific biomarker negative expansion cohort will be included in the efficacy analysis for the histology-agnostic biomarker negative expansion cohort, which will by definition be considered not active with 0-1 responses out of 10-20 subjects.

Note that the histology-agnostic biomarker negative expansion cohort may accrue prior to or in parallel with biomarker negative histology-specific expansion cohorts. Enrollment to the biomarker negative histology-agnostic cohort will continue while waiting to determine if this criteria applies. This criteria will only apply after at least 9 subjects on the

histology-specific biomarker cohort have discontinued treatment such that it is not possible to have ≥ 2 responses.

11.4 Methods of Analysis

Response criteria are described in [Section 12.0](#). A responder is defined as a patient who achieves a best response of PR or CR on the study. Response rates will be calculated as the percent of evaluable patients who are responders, and confidence intervals will be constructed using the Wilson score interval method.⁶¹ Decision making for A'Hern design cohorts will follow rules described above.

Any responses or lack thereof in patients enrolled during the determination of the Recommended Phase 2 Dose (dose finding phase) will count toward the objective response rate in their respective cohort.

Toxicity tables will be constructed to summarize the observed incidence by type of toxicity and grade. A patient will be counted only once for a given toxicity for the worst grade of that toxicity reported for that patient. Toxicity information recorded will include the type, severity, time of onset, time of resolution, and the probable association with the study regimen.

11.5 Evaluability for Response

Any eligible patient who is enrolled and receives at least one dose of protocol therapy on any APEC1621 subprotocol will be considered evaluable for response. Any patient who receives non-protocol anti-cancer therapy during the response evaluation period will be considered a non-responder for the purposes of the statistical rule, unless they show an objective response prior to receiving the non-protocol anti-cancer therapy (in which case they will be considered a responder). Patients who demonstrate a complete or partial response confirmed by central review will be considered to have experienced a response. All other patients will be considered non-responders. Patients who are not evaluable for response evaluation may be replaced for the purposes of the statistical rule. All patients considered to have a response (CR or PR) must have imaging studies reviewed centrally at the COG. Centers will be notified by the COG about requests for scans of patients with stable disease. Preliminary assessment of activity using institutionally provided tumor measurements will be entered into CDUS quarterly. The central review by COG will be provided as the final reviewed assessment of response when such becomes available.

11.6 Evaluability for Toxicity

Any patient who experiences a DLT at any time during protocol therapy is considered evaluable for toxicity. Patients without DLT who receive at least 85% of the prescribed dose per protocol guidelines and had the appropriate toxicity monitoring studies performed during cycle 1 are also considered evaluable for toxicity.

11.7 Progression free survival (PFS)

Progression free survival will be defined as time from the initiation of protocol treatment to the occurrence of any of the following events: disease progression or disease recurrence or death from any cause. All patients surviving at the time of analyses without events will be censored at their last follow-up date.

PFS along with the confidence intervals will be estimated using the Kaplan-Meier method. Patients with local calls of disease progression (i.e. calls made by the treating institution), will be counted as having had an event, even if the central review does not declare

progression. We will also report PFS based on central radiology review as a secondary analysis, if adequate number of disagreements in progressions exist between the treating institutions and the central radiology review to make such an analysis meaningful.

11.8 Correlative Studies

A descriptive analysis of pharmacokinetic (PK) parameters will be performed to define systemic exposure, drug clearance, and other pharmacokinetic parameters. The PK parameters will be summarized with simple summary statistics, including means, medians, ranges, and standard deviations (if numbers and distribution permit).

A descriptive analysis of the exploratory aims described in [Section 1.3](#) will be performed and will be summarized with simple summary statistics. All of these analyses will be descriptive in nature.

11.9 Gender and Minority Accrual Estimates

The gender and minority distribution of the study population is expected to be:

Racial category	Ethnicity				Total	
	Not Hispanic or Latino		Hispanic or Latino			
	Female	Male	Female	Male		
American Indian/Alaska Native	0	0	0	0	0	
Asian	0	0	0	0	0	
Native Hawaiian or Other Pacific Islander	0	0	0	0	0	
Black or African American	2	3	0	0	5	
White	6	10	2	1	19	
More than one race	0	0	0	0	0	
Total	8	13	2	1	24	

This distribution was derived from the demographic data for patients enrolled on recent COG Phase 2 trials.

12.0 EVALUATION CRITERIA

12.1 Common Terminology Criteria for Adverse Events (CTCAE)

The descriptions and grading scales found in the current version of the NCI Common Terminology Criteria for Adverse Events v5.0 (CTCAE) will be utilized for AE reporting. All appropriate treatment areas should have access to a copy of the current CTCAE v5.0. A copy of the CTCAE v5.0 can be downloaded from the CTEP website (<http://ctep.cancer.gov>).

12.2 Progression-Free Survival

Progression-free survival (PFS) is defined as the duration of time from start of subprotocol treatment to time of progression or death, whichever occurs first.

Development of new disease or progression in any established lesions is considered progressive disease, regardless of response in other lesions – e.g., when multiple lesions show opposite responses, the progressive disease takes precedence.

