12.4 Response Criteria for Patients with Solid Tumor and Measurable Disease

12.4.1 **Evaluation of Target Lesions**

Complete Response (CR):

Disappearance of all target and non-target lesions. Any pathological lymph nodes (whether target or non-target) must have reduction in short axis to <10 mm. If immunocytology is available, no disease must be detected by that methodology. Normalization of urinary catecholamines or other tumor markers if elevated at study enrollment (for patients with neuroblastoma).

Partial Response (PR):

At least a 30% decrease in the sum of the diameters of target lesions, taking as reference the

baseline sum diameters

Progressive Disease (PD):

At least a 20% increase in the sum of the diameters of target lesions, taking as reference the smallest sum on study (this includes the baseline sum if that is the smallest on study). In addition to the relative increase of 20%, the sum must also demonstrate an absolute increase of at least 5 mm. (Note: the appearance of one or more new lesions is also considered progressions). Note: in presence of SD or PR in target disease but unequivocal progression in non-target or non-measurable disease, the patient has PD if there is an overall level of substantial worsening in non-target disease such that the overall tumor burden has increased sufficiently to merit discontinuation of therapy

Stable Disease (SD):

Neither sufficient shrinkage to qualify for PR nor sufficient increase to qualify for PD, taking as reference the smallest sum diameters while on study

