12.4.2 Evaluation of Non-Target Lesions

Complete Response (CR):

Disappearance of all non-target lesions and normalization of tumor marker level. All lymph nodes must be non-pathological in size (<10 mm short axis)

Note: If tumor markers are initially above the upper normal limit, they must normalize for a patient to be considered in complete clinical response.

Non-CR/Non-PD:

Persistence of one or more non-target lesion(s) and/or maintenance of tumor marker level above the normal limits

Progressive Disease (PD):

Appearance of one or more new lesions and/or *unequivocal progression* of existing non-target lesions. *Unequivocal progression* should not normally trump target lesion status. It must be representative of overall disease status change, not a single lesion increase.

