12.4.3 Overall Response Assessment

Table 1: For Patients with Measurable Disease (i.e., Target Disease)

Target Lesions	Non-Target Lesions	New Lesions	Overall Response	Best Overall Response when Confirmation is Required*
----------------	--------------------	-------------	------------------	--

CR	CR	No	CR	≥ 28 days Confirmation
CR	Non-CR/Non-PD	No	PR	≥ 28 days Confirmation
CR	Not evaluated	No	PR	
PR	Non-CR/Non-PD/not evaluated	No	PR	
SD	Non-CR/Non-PD/not evaluated	No	SD	documented at least once ≥ 28 days from baseline
PD	Any	Yes or No	PD	no prior SD, PR or CR
Any	PD**	Yes or No	PD	
Any	Any	Yes	PD	

* See RECIST 1.1 manuscript for further details on what is evidence of a new lesion.
 ** In exceptional circumstances, unequivocal progression in non-target lesions may be accepted as disease progression.

Note: Patients with a global deterioration of health status requiring discontinuation of treatment without objective evidence of disease progression at that time should be reported as "*symptomatic deterioration*." Every effort should be made to document the objective progression even after discontinuation of treatment.

Table 2: For Patients with Non-Measurable Disease (i.e., Non-Target Disease)

Non-Target Lesions	New Lesions	Overall Response
CR	No	CR
Non-CR/non-PD	No	Non-CR/non-PD*
Not all evaluated	No	not evaluated
Unequivocal PD	Yes or No	PD
Any	Yes	PD

* 'Non-CR/non-PD' is preferred over 'stable disease' for non-target disease since SD is increasingly used as an endpoint for assessment of efficacy in some trials so to assign this category when no lesions can be measured is not advised

Table 3: Overall Response for Patients with Neuroblastoma and Measurable Disease

CT/MRI	MIBG	Bone Scan	Bone Marrow	Catechol	Overall
PD	Any	Any	Any	Any	PD
Any	PD	Any	Any	Any	PD
Any	Any	PD	Any	Any	PD
Any	Any	Any	PD	Any	PD
SD	CR/PR/SD	Non-PD	Non-PD	Any	SD
PR	CR/PR	Non-PD	Non-PD	Any	PR
CR/PR	PR	Non-PD	Non-PD	Any	PR
CR	CR	Non-PD	Non-PD	Elevated	PR
CR	CR	CR	CR	Normal	CR

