12.7.4 Response Criteria for Target Lesions

Response criteria are assessed based on the product of the longest diameter and its longest perpendicular diameter. Development of new disease or progression in any established lesions is considered progressive disease, regardless of response in other lesions – e.g., when multiple lesions show opposite responses, the progressive disease takes precedence. Response Criteria for target lesions:

- **Complete Response (CR):** Disappearance of all target lesions. Off all steroids with stable or improving neurologic examination.
- **Partial response (PR):** $\geq 50\%$ decrease in the sum of the products of the two perpendicular diameters of all target lesions (up to 5), taking as reference the initial baseline measurements; on a stable or decreasing dose of steroids with a stable or improving neurologic examination.
- **Stable Disease (SD):** Neither sufficient decrease in the sum of the products of the two perpendicular diameters of all target lesions to qualify for PR, nor sufficient increase in a single target lesion to qualify for PD; on a stable or decreasing dose of steroids with a stable or improving neurologic examination.
- **Progressive Disease (PD):** 25% or more increase in the sum of the products of the perpendicular diameters of the target lesions, taking as reference the smallest sum of the products observed since the start of treatment, or the appearance of one or more new lesions.

Increasing doses of corticosteroids required to maintain stable neurological status should be strongly considered as a sign of clinical progression unless in the context of recent wean or transient neurologic change due e.g. to radiation

effects.

12.7.5 Response Criteria for Non-Target Lesions:

- **Complete Response (CR):** Disappearance of all non-target lesions.
- **Incomplete Response/Stable Disease (IR/SD):** The persistence of one or more non-target lesions.
- **Progressive Disease (PD):** The appearance of one or more new lesions and/or unequivocal progression of existing non-target lesions.

12.7.6 Response criteria for tumor markers (if available):

Tumor markers will be classified simply as being at normal levels or at abnormally high levels.

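### Sections 12.2 and 12.7.4 call growth of any one lesion progression with no threshold, while 12.4 and the CNS PD bullet judge progression overall, so patients with several lesions can be classified two ways

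*Combined protocol and SAP*

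**What the plan says.** Section 12.2, which defines PFS, states: "Development of new disease or progression in any established lesions is considered progressive disease, regardless of response in other lesions". It adds that PD wins when lesions move in opposite directions. It gives no percentage or absolute increase and does not separate target from non-target lesions.

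For solid tumors outside the CNS:

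- Section 12.4.1 sets target-lesion PD as "At least a 20% increase in the sum of the diameters of target lesions", measured from the smallest sum on study, with an absolute rise of at least 5 mm.
- For non-target disease, 12.4.1 asks for an "overall level of substantial worsening in non-target disease such that the overall tumor burden has increased sufficiently" to justify stopping therapy.
- Section 12.4.2 says of non-target progression: "It must be representative of overall disease status change, not a single lesion increase".
- The note to Table 1 in 12.4.3 adds: "In exceptional circumstances, unequivocal progression in non-target lesions may be accepted as disease progression".

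For CNS tumors, 12.7.4 contains three statements. The lead-in says that "progression in any established lesions is considered progressive disease, regardless of response in other lesions". The SD bullet requires "nor sufficient increase in a single target lesion to qualify for PD". The PD bullet requires "25% or more increase in the sum of the products of the perpendicular diameters of the target lesions", measured from the smallest sum since treatment began.

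Section 12.3 says that RECIST 1.1 governs both response and progression. No passage says which rule prevails where they differ.

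**The concern.** A rule on a sum offsets growth in one lesion against shrinkage in another. A rule that makes any one lesion's progression decisive, whatever the others do, forbids that offset. Both are in force for the same patients. Within 12.7.4 they stand side by side, and the SD bullet is not the complement of the PD bullet.

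Three things depend on the choice:

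- **PFS dates.** Section 11.7 counts progression called by the treating institution even if central review disagrees. Section 8.2.1 lists responders and patients with six cycles of stable disease for central review, but not early PD. The central-review PFS analysis in 11.7 is conditional on enough disagreements.
- **Removal from therapy.** Section 10.1(a) takes patients off drug for PD.
- **CNS best response.** For CNS tumors the any-lesion sentence sits inside the response criteria, and Table 5 in 12.9.1 turns a PR followed by progression at the second assessment into a best response of PD.

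**Working it through.** The plan states no figure on this point, so there is none to reproduce. The lesion sizes below are assumed. Let t be the smallest growth of one lesion that counts as progression under 12.2. The plan gives no t, so each measured example shows the range of t over which the passages disagree.

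**1. Measured examples at the first scan (baseline is the smallest sum)**

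- Solid tumor, 40 + 15 mm to 40 + 21 mm. Sum: 61/55 − 1 = +10.9%, a rise of 6 mm, so SD under 12.4.1. Smaller lesion: 21/15 − 1 = +40%. Under 12.2 this is PD for any t up to 40%.
- Solid tumor, 60 + 12 mm to 30 + 18 mm. Sum: 48/72 − 1 = −33.3%, which meets the 30% decrease for PR. Smaller lesion: 18/12 − 1 = +50%. Under 12.2 this is PD for any t up to 50%.
- CNS, products 6 + 2 cm² to 6 + 3 cm². Sum: 9/8 − 1 = +12.5%, below 25%, so not PD by the PD bullet. Smaller lesion: 3/2 − 1 = +50%, so PD by the lead-in for any t up to 50%. If 25% is applied to the single lesion, the SD bullet is not met either, and the bullets leave the patient in no category.

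**2. Distance between the rules when lesions move in opposite directions**

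Take two equal targets at the first scan, one shrinking by s and the other growing by g. The sum changes by (g − s)/2.

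- RECIST percentage criterion: (g − s)/2 ≥ 0.20, so g ≥ 0.40 + s.
- CNS: (g − s)/2 ≥ 0.25, so g ≥ 0.50 + s.
- With s = 30%, the growing lesion must reach +70% in diameter (RECIST) or +80% in product (CNS) before the sum gives PD.

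With k equal targets and the others unchanged, g must reach 20% × k (RECIST) or 25% × k (CNS). That is 40% or 50% at k = 2, and 100% or 125% at k = 5.

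**3. An example without a measured threshold**

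One target goes from 40 to 26 mm (26/40 − 1 = −35%, PR) while one of several non-target lesions progresses. Sections 12.4.2 and Table 1 give PR and 12.2 gives PD, provided that progression in 12.2 means less than the unequivocal progression of 12.4.2.

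**4. Time at stake**

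Scans fall every second 28-day cycle, and a confirmatory scan follows a PR one cycle later (8.1, footnote 4). If the sum rule is met at the very next scan, the PFS date differs by 2 × 28 = 56 days for a patient called SD, or 28 days for one called PR. A PD call at the end of cycle 2 leaves up to (6 − 2) × 28 = 112 days of therapy not given.

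**5. What a plain pointer from 12.2 would do to MIBG-positive neuroblastoma**

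In 12.5.3, PD means new lesions only, and SD ends at a relative score of 1.0. A single site scored 1 that spreads to over half of its segment scores 3. If it is the only site, the relative score is 3/1 = 3.0 with no new lesion, which is neither SD nor PD. Table 4 does not resolve this. The any-lesion sentence in 12.2 is what now covers it.

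**The case against.** The best reply is that 12.2 cannot classify a scan by itself, because it has no threshold. Read with 12.3, it is then only a precedence statement: PD in one component overrides response in another. Table 1 already works that way, since target PD, non-target PD or a new lesion each gives PD whatever else responds. This has force for solid tumors, where a reader who knows RECIST may never meet the conflict. It also weakens example 3, because the passages agree if 12.2 means unequivocal progression. It does not rescue the text. A sum of target diameters cannot honor a rule that ignores response in other lesions, and no precedence reading explains three unaligned statements inside 12.7.4.

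It is also fair to say that two of those three CNS statements work lesion by lesion. A reader might infer that the sum rule is plainly what was intended for CNS tumors. The documents do not show that. It is only the rule with a stated threshold.

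The limits on impact stand. PFS is secondary, estimated descriptively and without a decision rule. By 12.7.3, most CNS tumors have one lesion. Sites may also call progression clinically (10.1(a)) and need not confirm it by imaging (8.1, footnote 4), so some variation between sites would remain after any amendment.

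A reader might further infer that the primary decision rule is undermined. If 5%, 10% or 20% of true responders were reclassified as PD, the power of the rule of at least 3 responses in 20 at a 25% response rate would fall from 0.909 to 0.887, 0.861 or 0.794. Nothing in the documents supports any of those shares, and outside the CNS the any-lesion sentence sits in the PFS section. The figures should not be used to raise the point's weight.

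**Conclusion.** The conflict is real for patients with more than one lesion, including a solid-tumor patient with one target plus non-target lesions. Section 12.2 and the 12.7.4 lead-in cannot be reconciled with the sum rule in 12.4.1, the overall-status requirement in 12.4.2 or the CNS PD bullet, and the CNS SD and PD bullets do not match each other. Patients with a single lesion are unaffected by the sum-versus-lesion difference. New lesions in solid and CNS tumors are PD under every passage.

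The consequence is possible misdating of local PFS events, possible early removal from therapy and, occasionally, a changed CNS best response. The 28 and 56 days assume that the sum rule is met at the next scheduled scan, and the 112 days is an upper bound. The measured examples depend on assumed lesion sizes and an assumed t. The number of patients affected cannot be derived and is probably small. The text should be corrected because the correction is cheap and few patients contribute to the PFS estimate (accrual is capped at 24), not because the main conclusion is in danger.

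**What to change.** **Section 12.2.** For patients assessed under 12.4, 12.7 or 12.8, say that progression is as defined in that section, which agrees with 12.3. For MIBG-positive neuroblastoma (12.5, with 12.6 for marrow), keep progression of established lesions as PD, for example by adding a relative score above 1.0 to the PD definition in 12.5.3. Without this, removing the sentence opens the gap shown in step 5.

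**Section 12.7.4.** Use one rule in all three places. The default is the sum of products from the smallest value on study: delete the any-lesion lead-in sentence and reword the SD bullet to refer to growth of the sum rather than of one target lesion. New lesions and unequivocal non-target progression (12.7.5) remain PD. If the study team intended a lesion-level rule for CNS tumors, it should instead state the single-lesion threshold in the PD bullet and align the other statements with it.

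**Cost.** This is a short wording amendment with two downsides. Under the sum rule, a multi-lesion CNS patient with one growing lesion may stay on drug longer: with five equal targets and the others unchanged, one could grow by just under 125% in product before the sum gives PD. Sections 10.1(a) and 10.1(f) still allow removal on clinical grounds. In addition, patients already taken off for single-lesion growth may lack later scans, and non-target lesions need not be measured, so some dates may not be recoverable. Those patients should be listed in the report.

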12.3 Response Criteria for Patients with Solid Tumors

See the table in [section 8.0](#) for the schedule of tumor evaluations. Eligible patients must have measurable disease present at baseline and have had their disease re-evaluated after one dose of protocol therapy. In addition to the scheduled scans, a confirmatory scan should be obtained on the next consecutive cycle following initial documentation of objective response.

As outlined, patients will be assigned to one of the following categories for assessment of response: a) solid tumor (non-CNS) and measurable disease ([Section 12.4](#)); b) neuroblastoma with MIBG positive lesions ([Section 12.5](#)); c) CNS tumor ([Section 12.7](#)); and d) non-Hodgkin lymphoma/histiocytosis ([Section 12.8](#)). Note: Neuroblastoma patients who do not have MIBG positive lesions should be assessed for response as solid tumor patients with measurable disease.

Response and progression will be evaluated in this study using the revised Response Evaluation Criteria in Solid Tumors (RECIST) guideline (version 1.1).⁶² Key points are that 5 target lesions are identified and that changes in the *largest* diameter (unidimensional measurement) of the tumor lesions but the *shortest* diameter of malignant lymph nodes are used in the RECIST v 1.1 criteria.

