11.0 STATISTICAL AND ETHICAL CONSIDERATIONS

11.1 Sample Size and Study Duration

APEC1621D will require a minimum of 4 evaluable patients and a maximum of 144 patients (up to 98 biomarker-positive patients and up to 46 biomarker-negative patients, allowing for 15% inevaluability). Assuming an enrollment rate of 4-6 biomarker positive patients per year, this subprotocol is expected to be completed within 8-12 years.

As of Amendment #5A, accrual will stop once 20 evaluable patients have been accrued in the study. APEC1621D will require a maximum of 24 patients (allowing for 15% inevaluability). Assuming an enrollment rate of 4-6 biomarker positive patients per year, this subprotocol is expected to be completed within 4-6 years.

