12.3.1 Definitions

12.3.1.1 Evaluable for objective response:

Eligible patients who receive at least one dose of protocol therapy will be considered evaluable for response. Evaluable patients who demonstrate a complete or partial response confirmed by central review before receiving non-protocol anti-cancer therapy will be considered a responder. All other evaluable patients will be considered non-responders.

12.3.1.2 Evaluable Non-Target Disease Response:

Eligible patients who have evaluable but not measurable disease and have received at least one dose of protocol therapy will be considered evaluable for non-target disease. The response assessment is based on

the presence, absence, or unequivocal progression of the lesions.

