12.8.4 Evaluation of organ enlargement⁶⁴

Complete Response (CR): Regress to normal

Partial response (PR): Spleen must have regressed by >50% in length beyond normal

Stable Disease (SD): No increase consistent with progression

Progressive Disease (PD): In the setting of splenomegaly, the splenic length must increase by 50% of the extent of its prior increase beyond baseline. If no prior splenomegaly, must increase by at least 2 cm from baseline.

New or recurrent splenomegaly

12.9 **Best Response**

Two objective status determinations of disease status, obtained on two consecutive determinations, separated by at least a 3 week time period, are required to determine the patient's overall best response. Two objective status determinations of CR before progression are required for best response of CR. Two determinations of PR or better before progression, but not qualifying for a CR, are required for a best response of PR. Two determinations of stable/no response or better before progression, but not qualifying as CR or PR, are required for a best response of stable/no response; if the first objective status is unknown, only one such determination is required. Patients with an objective status of progression on or before the second evaluations (the first evaluation is the first radiographic evaluation after treatment has been administered) will have a best response of progressive disease. Best response is unknown if the patient does not qualify for a best response of progressive disease and if all objective statuses after the first determination and before progression are unknown.

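### Does the re-evaluation clause in Section 12.3 let dosed but unassessed patients leave the response-rate denominator?

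*Combined protocol and SAP*

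**What the plan says.** Section 11.5 sets the response analysis set. "Any eligible patient who is enrolled and receives at least one dose of protocol therapy" counts as evaluable, and a patient without a centrally confirmed complete or partial response is a non-responder. A patient who takes other anti-cancer therapy before responding is also kept and counted as a non-responder. The section then adds: "Patients who are not evaluable for response evaluation may be replaced for the purposes of the statistical rule".

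Section 12.3.1.1, under the heading Definitions, repeats the rule: "Eligible patients who receive at least one dose of protocol therapy will be considered evaluable for response". It closes with "All other evaluable patients will be considered non-responders".

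Just before those definitions, the lead-in to Section 12.3 reads: "Eligible patients must have measurable disease present at baseline and have had their disease re-evaluated after one dose of protocol therapy".

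The denominator matters because of Section 11.4 ("Response rates will be calculated as the percent of evaluable patients who are responders") and Section 11.1 ("accrual will stop once 20 evaluable patients have been accrued in the study"). Section 12.9 adds a best-response category that has no explicit link to the rate: "Best response is unknown if the patient does not qualify for a best response of progressive disease" and no usable status follows the first determination. Table 5 in Section 12.9.1 has a similar label for patients whose second assessment was not done.

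**The concern.** The lead-in asks for something that neither definition asks for, namely a disease assessment after dosing. The replacement sentence in Section 11.5 does not list the patients it means. A reader could join the two and treat a dosed patient with no assessment as replaceable. The unknown and unclassifiable labels in Section 12.9 might encourage the same step for patients with only one assessment.

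Such patients can occur. Section 8.1 schedules tumor evaluation every other 28-day cycle, so a patient who leaves in the first 56 days may have no scan. Those patients are almost certainly non-responders. Replacing them would push the observed rate upward in a single-arm trial where one patient in 20 is worth 5 percentage points. It would also loosen the rule of at least 3 responses.

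**Working it through.** **1. The plan's own figures.** Inputs from Sections 11.3 and 11.3.1: N = 20, success at 3 or more responses, null rate 5%, target rate 25%, alpha 10%, power 90%. From Section 11.1: maximum 24 patients, allowing for 15% inevaluability.

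- Type I error = 1 − [0.95^20 + 20(0.05)(0.95^19) + 190(0.05²)(0.95^18)] = 1 − (0.35849 + 0.37735 + 0.18868) = 0.0755.
- Power = 1 − [0.75^20 + 20(0.25)(0.75^19) + 190(0.25²)(0.75^18)] = 1 − (0.00317 + 0.02114 + 0.06695) = 0.9087.
- Maximum enrollment: 20/0.85 = 23.5, rounded up to 24.

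The stated design is reproduced. The 10% is a ceiling, and the attained 7.55% lies below it, as is usual for an exact discrete rule.

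**2. Who falls where.**

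| Patient | Under 11.5 and 12.3.1.1 | If the 12.3 lead-in overrode them |
|---|---|---|
| Ineligible or never dosed | Not evaluable, replaceable | Same |
| Dosed, centrally confirmed response | Responder | Same |
| Dosed, fully assessed, no confirmed response | Non-responder, kept | Same |
| Dosed, one assessment only | Non-responder, kept | Kept: disease was re-evaluated; only the best-response label might suggest otherwise |
| Dosed, no assessment | Non-responder, kept | Could be called not evaluable and replaced |

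The replaceable group is therefore fixed as the complement of the evaluable group. It is not an empty category: Section 4.0 describes enrolled patients who fail a pre-treatment laboratory recheck and never receive drug.

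**3. Size of the misreading.** Suppose k dosed non-responders are replaced. The number of responses is unchanged but is drawn from 20 + k dosed patients, so type I error is P(X ≥ 3) for a binomial with n = 20 + k and p = 0.05.

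| Replaced (k) | n dosed | Type I error |
|---|---|---|
| 0 | 20 | 7.55% |
| 1 | 21 | 8.5% |
| 2 | 22 | 9.5% |
| 3 | 23 | 10.5% |
| 4 | 24 | 11.6% |

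The 10% ceiling is passed only at the third replacement. The largest excess is 11.6 − 10 = 1.6 points, and it needs all four spare places to go to dosed, unassessed patients.

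**4. By assumed frequency.** The documents give no rate of dosed patients without an assessment. Assume that 5%, 10%, 15% or 20% of dosed patients are unassessed, that none of them responds, and that at most 24 are dosed. Type I error under the misreading is then 8.5%, 9.5%, 10.4% or 11.0%.

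**5. Effect on the estimate.** The 90% Wilson interval has centre (p̂ + z²/2n)/(1 + z²/n) and half-width z√[p̂(1 − p̂)/n + z²/4n²]/(1 + z²/n), with z = 1.645. At the extreme, 3 responders among 24 dosed is 12.5% (5.1% to 27.5%). Dropping four unassessed patients would report 3/20 = 15.0% (6.2% to 32.2%).

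**The case for a change.** The best argument for acting is that the lead-in qualifies the word eligible, and both definitions begin from eligible patients. Post-dose re-evaluation cannot be an enrollment criterion, so the sentence might be read as defining who is eligible for response assessment. On that reading it narrows the definitions without openly contradicting them. The replacement sentence is also permissive, and the study chair enters evaluability in a single-arm trial where outcomes may be known. Stating the replaceable group outright would take two sentences.

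Part of this stands. The clause does not fit the one-dose rule. The lead-in is loose in another way too: it asks for measurable disease although Section 4.1.4 admits neuroblastoma with MIBG-positive disease only. Section 12.3 itself then sends those patients to the MIBG criteria in Section 12.5.

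The rest does not carry. Eligibility is fixed in Section 4 before any post-dose scan exists. The lead-in does not mention evaluability, the denominator or replacement, while the text headed Definitions just below it settles evaluability in terms. The labels in Section 12.9 describe best response, not membership of the analysis set. Section 11.4 defines a responder as a patient with a best response of PR or CR, so patients with those labels are already non-responders. Section 14.4.2 has the MATCH Chair, Vice Chair and Statistician review the study chair's evaluations weekly, which limits the room for an isolated misreading.

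**Conclusion.** The mismatch is real but clerical, and no change to the plan follows. Two matching definitions keep every eligible dosed patient in the denominator, including those unassessed, unknown or unclassifiable. They leave only ineligible or never-dosed patients to be replaced. On that basis the primary analysis has the properties claimed for it: type I error 7.55%, within the 10% ceiling, and power 90.9%. Trimming the clause would alter neither N, the decision rule, nor the planned response rate.

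The upward bias would arise only if an introductory sentence displaced both definitions. Even then type I error would stay below 10% with one or two replacements and could not exceed 11.6%. These conditional figures assume that every replaced patient is a non-responder. The frequency-based figures also rest on assumed shares of unassessed patients, which the documents do not supply.
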